## 6.9. Multiplicity Considerations

It is recognized that with a multiplicity of tests comes an inflation in the chance of a false finding of superiority or non-inferiority. Therefore, for the purpose of seeking approved labeling claims on designated secondary objectives, the following standard will be used: if the primary objective demonstrates non-inferiority, claims will be sought for selected secondary non-inferiority and superiority objectives and for superiority on the primary objective metric. These will be tested via a hierarchical (sequential) testing order that preserves the overall study-wise type I error rate at the level of 0.05. The testing order is specified below. The following secondary objectives are tested in order, and testing continues if and only if all previous objectives have met their designated success criterion.

1. Transvalvular mean gradient at 1 year (non-inferiority)
2. Effective orifice area at 1 year (non-inferiority)
3. Change in NYHA classification from baseline to 1 year (non-inferiority)
4. Change in KCCQ score from baseline to 1 year (non-inferiority)
5. Transvalvular mean gradient at 1 year (superiority)
6. Effective orifice area at 1 year (superiority)
7. Change in KCCQ score from baseline to 30 days (superiority)

This document is electronically controlled. Printed copies are considered uncontrolled.

**Confidential**

All of the above non-inferiority will be tested with a type I error standard of 0.05 and superiority tests will be tested with a type I error standard of 0.025. If all of the above tests meet their success criterion, the primary endpoint (superiority) will be tested using a type I error rate of 0.025.

For the purposes of seeking claims, these objectives will only be evaluated once, at the same time as non-inferiority of the primary objective is established. The only exception to this is the primary endpoint superiority test, which carries the possibility of a delayed determination of superiority and may thus meet its success criterion at a different time (see Section 6.5.2).

The remaining secondary endpoints (see Section 3.2 and Section 3.3) may be of interest for scientific reasons but will not be the basis for supporting labeling claims; they are thus outside of the hierarchical testing procedure. Similarly, for those objectives that test non-inferiority, if non-inferiority is established, a test of superiority may also be conducted, but unless specifically itemized in the list, such superiority testing is not part of the hierarchical testing procedure; these superiority tests may be of interest for scientific reasons but will not be the basis for supporting labeling claims.

### 6.9.1. Ordered List of Secondary Objectives to be Tested to Support Labeling Claims

1. Transvalvular mean gradient at 1 year (non-inferiority). The hypothesis of interest is

$$H: \mu_{TAVR} < \mu_{SAVR} + 5$$

where  $\mu_{TAVR}$  and  $\mu_{SAVR}$  denote the average mean gradient at 1 year, measured in mmHg. This objective will be evaluated using a Bayesian version of a two-sample t-test. The posterior probability  $P(H | \text{data})$  will be calculated and compared to a threshold of 0.95.

**Rationale for Delta:** A difference less than 5 mmHg for mean gradient is not considered clinically relevant for the TAVR Low Risk Executive Committee.

2. Effective orifice area at 1 year (non-inferiority). The hypothesis of interest is

$$H: \mu_{TAVR} > \mu_{SAVR} - 0.1$$

where  $\mu_{TAVR}$  and  $\mu_{SAVR}$  denote the mean effective orifice area at 1 year, measured in  $\text{cm}^2$ . This objective will be evaluated using a Bayesian version of a two-sample t-test. The posterior probability  $P(H | \text{data})$  will be calculated and compared to a threshold of 0.95.

**Rationale for Delta:** A difference less than 0.1  $\text{cm}^2$  for effective orifice area is not considered clinically relevant for the TAVR Low Risk Executive Committee.

3. Change in NYHA classification from baseline to 1 year (non-inferiority). The hypothesis of interest is

$$H: \mu_{TAVR} > \mu_{SAVR} - 0.375$$

where  $\mu_{TAVR}$  and  $\mu_{SAVR}$  denote the mean number of classification improvements in NYHA from baseline to 1 year. For subjects with NYHA categories at both baseline and 1-year visit, the NYHA classification improvements will be calculated as  $\text{NYHA}_{\text{baseline}} - \text{NYHA}_{12\text{month}}$ . The objective will be evaluated using a Bayesian version of a two-sample t-test. The posterior probability  $P(H | \text{data})$  will be calculated and compared to a threshold of 0.95.

**Rationale for Delta:** A difference less than 0.375 for NYHA classification is not considered clinically relevant for the TAVR Low Risk Executive Committee.

4. Change in Kansas City Cardiomyopathy Questionnaire (KCCQ) score from baseline to 1 year (non-inferiority). The hypothesis of interest is

$$H: \mu_{TAVR} > \mu_{SAVR} - 5$$

where  $\mu_{TAVR}$  and  $\mu_{SAVR}$  denote the mean changes in the KCCQ score from baseline to 1 year. For subjects with KCCQ score at both baseline and 1 year, the change in KCCQ will be calculated as  $\text{KCCQ}_{1\text{year}} - \text{KCCQ}_{\text{baseline}}$ . The objective will be evaluated using a Bayesian version of a two-sample t-test. The posterior probability  $P(H | \text{data})$  will be calculated and compared to a threshold of 0.95.

This document is electronically controlled. Printed copies are considered uncontrolled.

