### 3.3.8 Screening, Enrollment, and Randomization

The process of patient screening, subject enrollment, and randomization is as follows (Figure 1):

1. Patients identified by or presented to the trial site with aortic stenosis will be screened by the investigative team for the criteria described in 3.3.5, Subject Selection Criteria, using available medical records, including relevant imaging studies previously performed for diagnostic purposes.
2. If the patient is deemed a potential candidate for the trial, the investigational status of the Medtronic TAVR System and all aspects of the trial will be explained to the patient. The patient will then be invited to participate in the Low Risk Trial. Sites participating in the LTI Sub-study will also invite patients to consent for the LTI Sub-Study.
3. If the patient agrees to participate, written informed consent will be obtained. This will be considered the point of enrollment, and the subject will be assigned a Subject ID number.
4. The subject will undergo transthoracic echocardiography (TTE) to assess his/her degree of aortic stenosis.
5. Subjects who meet the criteria for aortic stenosisiii will undergo:
  - a. Multi-Detector Computed Tomography (MDCT) of their peripheral vasculature and aortic annulus to assess anatomic suitability for the Medtronic TAVR, and
  - b. Local Heart Team assessment to determine his/her operative risk profile for SAVR.
6. If the local Heart Team considers the subject anatomically suitable for implantation and at low risk for SAVR, the subject's clinical information will be submitted to the Screening Committee. The Heart Team assessment must be documented. The following information should be submitted to the Screening Committee:
  - Clinical assessments including STS-PROM, medical history and co-morbidities
  - TTE data on degree of aortic stenosis
  - MDCT data on anatomical suitabilityiv
7. The Screening Committee will review the clinical information to confirm the eligibility of the subject for implantation.

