Where:  $VTI_{V1}$  is the velocity time integral of the left ventricular outflow tract in cm, and  $VTI_{V2}$  is the velocity time integral of the native aortic valve in cm
- **Aortic Valve Area Index (AVAI) in  $\text{cm}^2/\text{m}^2$**   
AVAI = AVA/BSA  
Where: AVA is the native aortic valve area in  $\text{cm}^2$ , and BSA is the body surface area in  $\text{m}^2$ x
- **Effective Orifice Area (EOA) in  $\text{cm}^2$**   
EOA = LVOT diameter  $\times 0.785 \times (VTI_{V1}/VTI_{V2})$   
Where:  $VTI_{V1}$  is the velocity time integral of the left ventricular outflow tract in cm, and  $VTI_{V2}$  is the velocity time integral of the aortic prosthesis in cm
- **Effective Orifice Area Index (EOAI) in  $\text{cm}^2/\text{m}^2$**   
EOAI = EOA/BSA  
Where: EOA is the effective orifice area in  $\text{cm}^2$ , and BSA is the body surface area in  $\text{m}^2$
- **Doppler Velocity Index (DVI)**  
DVI =  $VTI_{V1}/VTI_{V2}$   
Where:  $VTI_{V1}$  is the velocity time integral of the left ventricular outflow tract in cm, and  $VTI_{V2}$  is the time velocity integral of the prosthetic aortic valve in cm
- **Left Ventricular Mass (LVM) in grams**  
LVM =  $0.83 \times [(LVIDD + LVPW + IVS)^3 - (LVIDD)^3] + 0.6$   
Where: LVIDD is the left ventricular internal dimension at end diastole in cm, LVPW is the left ventricular posterior wall thickness at end diastole in cm, and IVS is the interventricular wall thickness at end diastole in cm.
- **Left Ventricular Mass Index (LVMI) in  $\text{g}/\text{m}^2$  body surface area**  
LVMI = LVM/BSA  
Where: LVM is left ventricular mass in g, and BSA is body surface area in  $\text{m}^2$
- **Estimated Right Ventricular Systolic Pressure (RVSP) in mmHg**  
RVSP =  $(4 \times MVTR \text{ jet}^2) + 10$   
Where: MV TR jet is the max velocity of the tricuspid regurgitant jet, and 10 = the assumed mean right atrial pressure in mmHg
- **Body Surface Area (BSA) in  $\text{m}^2$**   
BSA =  $0.007184 \times (\text{height in cm})^{0.725} \times (\text{weight in kg})^{0.425}$

---

x BSA derived from height and weight reported on the site eCRF

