**Confidential**

- Mean aortic gradient < 20 mmHg or peak velocity < 3 m/sec;
- Absence of moderate or severe prosthetic valve regurgitation. Total Aortic Prosthetic Regurgitation on the ECHO CORE LAB form not equal to moderate or severe.

All of the above components must be satisfied to count as a device success. If any of the above components fails, the endpoint will be counted as a failure.

For the overall device success rate, the numerator will be the number of subjects whose procedures result in device success as described above, and the denominator will be the number of subjects whose device success results are not missing (either success or failure). Note that this analysis excludes those subjects with a missing response to any of the above five components (eg, the field “Post-implant Severity of Total Aortic Regurgitation”=“Unable to Assess” or “Not Recorded”, missing mean aortic gradient, or missing peak velocity, etc.) and without a “NO” response to any of the components.

- Hemodynamic performance metrics by Doppler echocardiography
  - Mean aortic gradient at one year
  - Effective orifice area at one year
  - Degree of total, peri, and transvalvular prosthetic regurgitation at one year

For mean gradient and effective orifice area, the descriptive statistics will be reported at each of the assessed time point (30 days, 6 months, one year, 2 years, 3 years, 4 years, 5 years, 7 years and 10 years). The statistical method will be the Bayesian version of a two-sample t-test.

Prosthetic regurgitation severity will be reported as proportions at each of the assessed time point (30 days, 6 months, one year, 2 years, 3 years, 4 years, 5 years, 7 years and 10 years). The statistical method will be the Bayesian version of a comparison of proportions.

- New York Heart Association (NYHA) functional classification at one year

NYHA function classification will be reported as proportions at each of the assessed time point (30 days, 6 months, one year, 2 years, 3 years, 4 years, 5 years, 7 years and 10 years). The statistical method will be the Bayesian version of a comparison of proportions.

- Health-related quality of life as assessed by EQ-5D survey instrument at one year.

The endpoint will be evaluated using a Bayesian analog of a two-sample t-test.

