**Confidential**

**Rationale for Delta:** A 5-point improvement or decrease in KCCQ is the minimum difference that is clinically relevant.

5. Transvalvular mean gradient at 1 year (superiority). The hypothesis of interest is

$$H: \mu_{TAVR} < \mu_{SAVR}$$

where  $\mu_{TAVR}$  and  $\mu_{SAVR}$  denote the average mean gradient at 1 year, measured in mmHg. This objective will be evaluated using a Bayesian version of a two-sample t-test. The posterior probability  $P(H | \text{data})$  will be calculated and compared to a threshold of 0.975.

6. Effective orifice area at 1 year (superiority). The hypothesis of interest is

$$H: \mu_{TAVR} > \mu_{SAVR}$$

where  $\mu_{TAVR}$  and  $\mu_{SAVR}$  denote the mean effective orifice area at 1 year, measured in  $\text{cm}^2$ . This objective will be evaluated using a Bayesian version of a two-sample t-test. The posterior probability  $P(H | \text{data})$  will be calculated and compared to a threshold of 0.975.

7. Change in Kansas City Cardiomyopathy Questionnaire (KCCQ) score from baseline to 30 days (superiority). The hypothesis of interest is

$$H: \mu_{TAVR} > \mu_{SAVR}$$

where  $\mu_{TAVR}$  and  $\mu_{SAVR}$  denote the mean changes in the KCCQ score from baseline to 30 days. For subjects with KCCQ score at both baseline and 30 days, the change in KCCQ will be calculated as  $\text{KCCQ}_{30\text{day}} - \text{KCCQ}_{\text{baseline}}$ . The objective will be evaluated using a Bayesian version of a two-sample t-test. The posterior probability  $P(H | \text{data})$  will be calculated and compared to a threshold of 0.975.

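### The two effective orifice area gates (SAP 6.9.1, items 2 and 6) leave out a pre-implant size covariate that is already measured in both arms, giving up precision at little saving

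*SAP*

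**What the plan says.** SAP 6.9.1 sets up item 2 (non-inferiority) and item 6 (superiority) on means that "denote the mean effective orifice area at 1 year, measured in" cm². For both, "This objective will be evaluated using a Bayesian version of a two-sample t-test". SAP 6.8 repeats this for the haemodynamic endpoints: "The statistical method will be the Bayesian version of a two-sample t-test". No covariate is named in either place. Covariate models appear only in the poolability analyses of the primary endpoint (SAP 6.10), and that list contains neither annulus nor LVOT size.

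The item 2 margin rests on the statement that "A difference less than 0.1" cm² is not clinically relevant. On error rates, SAP 6.9 says "All of the above non-inferiority will be tested with a type I error standard of 0.05". The superiority items are held to 0.025, and the corresponding posterior thresholds are 0.95 and 0.975. The list is tested in strict order, each item once, when primary non-inferiority is established. Primary superiority comes after all seven items.

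On size, Protocol Appendix I, section 5.0 derives "EOA = LVOT diameter" squared, times 0.785, times the ratio of LVOT to prosthesis velocity-time integrals (VTI). Protocol 3.3.8 requires an MDCT "of their peripheral vasculature and aortic annulus to assess anatomic suitability for the Medtronic TAVR", and Protocol 3.3.9 places MDCT and echocardiography before Screening Committee submission, hence before randomisation. Protocol 3.3.15 ties the qualifying valve area to pre-implant LVOT diameter, and the core lab also reports LVOT diameter (Appendix I, 5.0). Randomisation is stratified by site and need for revascularisation (SAP 6.1), not by size.

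**The concern.** LVOT diameter enters EOA as a square, so some of the between-subject spread in one-year EOA reflects anatomy fixed before randomisation. An unadjusted comparison counts that spread as noise and lets any chance imbalance in size feed into the estimate. The covariate is already collected, so omitting it saves very little.

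The stakes come from the testing order. Failing item 2 stops items 3 to 7 and primary superiority. Failing item 6 stops item 7 and primary superiority. Neither item can be repeated at a later look, and the plan states no SD, sample size or power for either.

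**Working it through.** **The plan's own figure.** The only sample-size calculation concerns the primary endpoint: 1032 for 15% versus 15%, margin 0.06, α = 0.05, power 85% (SAP 5.2). With Farrington-Manning restricted null rates of 0.1248 and 0.1848:

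n per arm = [1.645 × sqrt(0.1848×0.8152 + 0.1248×0.8752) + 1.036 × sqrt(2×0.15×0.85)]² / 0.06² = 515.2, so 516 per arm and 1032 in total.

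This reproduces exactly with α one-sided. There is no corresponding figure for EOA to reproduce.

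**Inputs for the EOA gates.**
- From the documents: margin 0.1 cm²; one-sided 0.05 (item 2) and 0.025 (item 6); first look at 850 subjects with 12 months of follow-up, second at 1200.
- Evaluable per arm: 850 × 0.94 / 2 ≈ 400. The 6% is the plan's allowance for missing primary data (Protocol 3.3.3.8); none is stated for unreadable echoes.
- Assumed, because not stated: EOA SD 0.4 to 0.7 cm², and R², the share of EOA variance explained by the pre-implant covariate.

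**Range for R².** From the formula, log EOA is a constant plus 2 log(D) plus log(VTI ratio). If the two factors are independent,

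R² = ρ² × 4 ln(1+CV_D²) / [4 ln(1+CV_D²) + ln(1+CV_V²)],

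where ρ is the correlation between pre- and post-implant LVOT diameter. With assumed CV_D 7–11%, CV_V 15–30% and ρ 0.5–0.9, R² runs from 0.05 to 0.55. A middle case (9%, 20%, 0.7) gives 0.22.

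**Effect on precision.** The standard error is multiplied by sqrt(1 − R²): 0.975 at R² = 0.05, 0.894 at 0.20 and 0.707 at 0.50. At R² = 0.20 this is worth 1/(1 − 0.20) = 1.25 times the subjects.

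**Power.** With SE = SD × sqrt(2(1 − R²)/n) and true difference d (TAVR minus SAVR), normal approximation with flat priors:
- item 2: Φ((0.1 + d)/SE − 1.645)
- item 6: Φ(d/SE − 1.960)

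At n = 400, SD 0.5, R² = 0: SE = 0.5 × sqrt(2/400) = 0.0354. Item 2 at d = 0 is Φ(2.828 − 1.645) = 88.2%. Item 6 at d = +0.1 is Φ(2.828 − 1.960) = 80.7%.

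| n per arm | SD | Item 2, d = 0: R² 0 / 0.2 / 0.4 | Item 6, d = +0.1: R² 0 / 0.2 / 0.4 |
|---|---|---|---|
| 400 | 0.4 | 97.1 / 99.0 / 99.8 | 94.2 / 97.7 / 99.5 |
| 400 | 0.5 | 88.2 / 93.5 / 97.8 | 80.7 / 88.5 / 95.5 |
| 400 | 0.6 | 76.2 / 83.9 / 91.9 | 65.4 / 75.0 / 86.1 |
| 400 | 0.7 | 64.6 / 73.0 / 83.2 | 52.4 / 61.7 / 74.2 |
| 340 (850 less an assumed 20%) | 0.5 | 83.2 / 89.8 / 95.7 | 74.1 / 83.0 / 92.0 |
| 564 (1200 less 6%) | 0.5 | 95.7 / 98.3 / 99.6 | 91.9 / 96.4 / 99.1 |

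At the ends of the R² range (n = 400, SD 0.5), item 2 is 89.6% at R² = 0.05 and 99.1% at 0.50; item 6 is 82.7% and 97.9%.

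**Where the gain disappears.** At n = 400 and SD 0.4 to 0.7, unadjusted power is already at least 99.2% for item 2 if d = +0.1, and at least 98.1% for item 6 if d = +0.2. Adjustment then adds 2 points or less.

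**The case against.** The unadjusted test is valid, pre-specified, simple, and the same method as for the other gates. That stands: type I error is unaffected, no passages conflict, and this is a matter of efficiency.

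A reader might infer that body and annulus size largely set orifice area. The documents do not support that. They make LVOT size one factor in a formula and give no correlation. The R² range above also assumes that LVOT diameter and VTI ratio are independent, and SAP 6.8 (note 3 to the valve dysfunction table) hints otherwise: the Doppler velocity index cut-off drops from 0.25 to 0.2 when LVOT diameter exceeds 2.5 cm. Suppose the correlation between true LVOT diameter and VTI ratio is −0.3, with true diameter 2.1 cm (SD 0.15–0.20), measurement error 0.08–0.10 cm and VTI-ratio CV 18–22%. R² is then about 0.07 to 0.30; at −0.5 it is about 0.02 to 0.22. So the gain could be small.

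A reader might also infer that weak power at item 2 under no true difference puts the primary superiority claim at risk. It does not. If EOA is truly equal, item 6 passes only about 2.5% of the time under any model, so primary superiority is blocked there anyway. In that scenario better item 2 power helps only items 3 to 5. The link to primary superiority runs through item 6, when TAVR has a modest true advantage.

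Other points bear on size, not direction. The sizing matrix (Protocol Appendix II, 4.0) covers only the transcatheter valve, while surgical valves may be any commercially available bioprosthesis, so one R² for both arms is an assumption. EOA is analysed in implanted subjects with a usable echo, a post-randomisation subset, but the unadjusted test uses the same subset. In a 1:1 comparison, a pre-implant covariate does not raise the large-sample standard error.

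**Conclusion.** The point holds as a recommended improvement, not as an error. Both EOA gates are unadjusted, each gets one attempt, and a relevant size measure exists in both arms before randomisation. At 400 per arm, SD 0.5 and R² = 0.20, adjustment is worth about 5 points at item 2 (no true difference) and about 8 points at item 6 (true +0.1 cm²). Across the assumed SDs and R² of 0.2 to 0.4, the item 2 gain at 400 per arm runs from about 2 points (SD 0.4, R² 0.2) to about 19 points (SD 0.7, R² 0.4). It is 2 points or less if TAVR's true advantage is 0.1 cm² (item 2) or 0.2 cm² (item 6). The SD, R² and true difference are all assumptions, so the documents settle the direction of the gain but not its size.

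**What to change.** Before the first interim lock, amend SAP 6.9.1 items 2 and 6, with a matching line in SAP 6.8:

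- Fit a Bayesian normal linear model for one-year EOA with treatment and one named pre-implant covariate. Compare the posterior probability that the treatment coefficient exceeds −0.1 with 0.95 (item 2), and that it exceeds 0 with 0.975 (item 6). Hypotheses, margin and thresholds stay as they are.
- Choose the covariate now. Core-lab baseline LVOT diameter is a natural choice, because it is read centrally from an echo within 12 weeks of submission. MDCT annulus perimeter is the alternative, but the scan may be up to 365 days old and either systolic or diastolic measurement is accepted.
- Exclude post-implant LVOT diameter explicitly. It is part of EOA and is measured differently by arm (Appendix I, 4.1).
- Give a simple rule for a missing covariate value, such as the overall mean across both arms.
- Report the unadjusted comparison as supportive, and state the assumed SD and power for both gates.

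The cost is SAP wording and some programming, with no new data collection. The model targets the same difference in means.

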**Confidential**

**Rationale for Delta:** A 5-point improvement or decrease in KCCQ is the minimum difference that is clinically relevant.

5. Transvalvular mean gradient at 1 year (superiority). The hypothesis of interest is

$$H: \mu_{TAVR} < \mu_{SAVR}$$

where  $\mu_{TAVR}$  and  $\mu_{SAVR}$  denote the average mean gradient at 1 year, measured in mmHg. This objective will be evaluated using a Bayesian version of a two-sample t-test. The posterior probability  $P(H | \text{data})$  will be calculated and compared to a threshold of 0.975.

6. Effective orifice area at 1 year (superiority). The hypothesis of interest is

$$H: \mu_{TAVR} > \mu_{SAVR}$$

where  $\mu_{TAVR}$  and  $\mu_{SAVR}$  denote the mean effective orifice area at 1 year, measured in  $\text{cm}^2$ . This objective will be evaluated using a Bayesian version of a two-sample t-test. The posterior probability  $P(H | \text{data})$  will be calculated and compared to a threshold of 0.975.

7. Change in Kansas City Cardiomyopathy Questionnaire (KCCQ) score from baseline to 30 days (superiority). The hypothesis of interest is

$$H: \mu_{TAVR} > \mu_{SAVR}$$

where  $\mu_{TAVR}$  and  $\mu_{SAVR}$  denote the mean changes in the KCCQ score from baseline to 30 days. For subjects with KCCQ score at both baseline and 30 days, the change in KCCQ will be calculated as  $\text{KCCQ}_{30\text{day}} - \text{KCCQ}_{\text{baseline}}$ . The objective will be evaluated using a Bayesian version of a two-sample t-test. The posterior probability  $P(H | \text{data})$  will be calculated and compared to a threshold of 0.975.

